conditioning. Each exercise can be modified to meet the needs of individual participants. The classes will be conducted by certified personal trainers. This control group was selected because of its past use as a control condition for Hatha yoga. This type of exercise program was comparable to Hatha yoga in terms of gains in functional fitness (Gothe & McAuley, 2016) but less effective at improving cognition (Gothe, Kramer, & McAuley, 2014) in community-dwelling samples of older adults.

Analytic Plan

Descriptive statistics will be obtained for all variables, including distributions, means, medians, variances, standard deviations, skewness, kurtosis, ranges, and quartiles. Tests of normality of continuous measures will be made using the Shapiro-Wilk W and the Kolomogorov D statistics in conjunction with plots of the distribution of data and descriptive measurements. The data will also be examined for homogeneity of variance. An appropriate statistical method will be employed to correct for any abnormalities. Missing data values will be minimized by intensive training of the assessors in techniques of clarifying answers and checking questionnaires while participants are on-site. When missing values are identified, we will employ several approaches to reduce their influences. If at all possible, participants will be rescheduled or a telephone call will be made within 24 hours of completion of tests or interviews. The pattern of missing data will be examined according to the procedure recommended by Little and Rubin (1987), which includes comparing group differences in the primary outcomes of subjects with versus without missing data. We will also test whether the drop-outs are random or systematic by comparing the drop-outs with the study completers on the baseline data. An absence of significant differences would support the random nature of drop-outs. Effect of drop-outs will be minimized by including all subjects in the analyses and by including any effect of systematic differences between the drop-outs and completers in the model as a covariate when applicable.

Each outcome variable will be graphed versus time for each subject for all available time points (baseline, mid-treatment, post-treatment, follow-up) to evaluate what function of time best describes the data. Hypotheses 1a and 1b will be tested using the Mixed Effect Model (Hedeker, Gibbons, & Waternaux, 1999). This method is robust with respect to drop-out and missing data. These mixed models allow us to assess whether important estimates are dependent on missing data patterns, and provide overall estimates of effects by averaging over the various missing-data patterns (Hedeker et al., 1999). In addition, we will use the extension of the Pattern-Mixture Models (Guo, Ratcliffe and Ten Have, 2004), which allows subject-to-subject heterogeneity and assess if there is bias due to drop out or missing data. The Mixed Effect method has several advantages over more traditional analytic approaches such as a change score, end-point or repeated measures analysis of variance. It allows the inclusion of subjects with missing data or those who were terminated early in the study, without relying on data imputation procedures. This method provides an estimate of the individual variability around the population trend, the variability of the individual intercepts (baseline values) and slopes (changes across time), and the correlation between them. We will include a random intercept, a random effect for assessment time, and fixed effects for comparison groups and group-by-time interaction in the model. A fully saturated treatment by time model will be utilized for inference. Co-variance structure will be chosen based on Akaike's Information Criterion (AIC). Random group level treatment effects will also be evaluated for importance based on the model AIC. This allows for any group level effects to be incorporated into the model. Denominator degrees of freedom will be calculated using the Kenward-Roger small sample correction. Statistical significance will be determined by $p < .05$ for hypothesis 1a and $p < .01$ (.05/5 to correct for multiple comparisons) for hypothesis 1b.

Hypotheses 2a.1, 2a.2, 2b.1 and 2b.2 initially will be tested using the same mixed model procedure identified in Hypothesis 1a and 1b. To test for mediation effect, we will utilize the analytic strategy described by Krull and MacKinnon (1999, 2001). In this approach, four conditions must be met: a) a significant relationship between the independent variable (treatment) and the dependent variable (PTSD symptoms as measured by CAPS), b) a significant relationship between the independent variable and the proposed mediator (Attention Model: mindfulness and attentional control; Coping Model: tolerance of discomfort and coping), c) a significant relationship between the mediators and the outcome, and d) the relationship between the independent variable and outcome must be significantly lower after controlling for the proposed mediator. The multiple-mediation model includes a multiple-path mediating effect through both mediators (i.e. mindfulness and attentional control or tolerance of discomfort and maladaptive coping), which allows one mediator (e.g., mindfulness) to causally affect the other mediator (e.g., attentional control). Multimodal assessment is used for Attentional Control, Tolerance of Discomfort and Coping based on the theoretical models discussed previously. The relation among these variables and their individual contribution to the construct of interest will be examined in order to

remove variables or create composites. Correlation coefficients among the outcomes for each mediator will be examined. Furthermore, the main effect of each outcome will be examined in the mixed effect model. Low correlated outcomes or outcomes that are highly (greater than .8) correlated with each other and/or low contribution in the model will be considered to be dropped from the model. The effect of mediators in the model can be calculated based on either the difference between two regression parameters ($\tau - \tau^2$) or the multiplication of two regression parameters ($\alpha\beta$) (MacKinnon, Warsi, & Dwyer, 1995). The variance estimates produced by the various methods are quite similar to each other and to the true value of the variance in situations involving continuous multivariate normal data and a continuous independent variable (MacKinnon et al., 1995). Although there is some evidence that the least model in the case-control study design setting this approach could provide biased estimations for the indirect effects (Wang et al., 2012), we believe the Sobel (1982) procedure to test for significant mediation is most appropriate approach for this study. Next we will use the formula provided by MacKinnon and Dwyer (1993) to determine the percentage of the intervention condition to primary outcome path that was accounted for by change in our mediator. We acknowledge that this method may not be supportable given the need to reduce sample size. If the study biostatistician determines that this is the case, she will utilize other strategies to analyze available data and generate testable hypotheses for future studies. The exploratory aim will be analyzed using similar approach. Data will be analyzed from all randomized subjects on whom we have a baseline assessment and at least one post-baseline evaluation. All statistical tests will be two-tailed. We will adjust p-values for multiple testing as appropriate.

Sample size. We used the method provided by Hedeker, Gibbons, & Waternaux (1999) for the Random Regression Model and the RMASS program provided by Hedeker (2016) to estimate needed sample size for Aim 1. Medium effect size was selected based on finding from previous yoga trials (Wells et al., 2016) and was defined as a between-group difference increasing linearly from 0 at baseline to .5 SD units at the last time point. The minimum power estimation is based on sample size calculation for 10% and 20% attrition, correlations of 0.2, 0.5, and 0.8 between the repeated measures, and for medium and large effect sizes. We are confident that with the proposed total sample size of at least 48/arm would be sufficient to achieve a minimum 80% power for the primary aim.

Management

Management of this single-site study will be [name] responsibility. She has considerable experience in research management from small developmental grants (e.g., NCCIH R34) to a large multi-site consortium (INTRuST PTSD/TBI Clinical Consortium Deputy Director) and center of excellence (VASDHS CESAMH Associate Director). Administrative aspects of the project will be supported by [name], who has been [name] lead coordinator for more than a decade. [name] will coordinate scientific aspects of the project, holding regular meetings with the investigative team. [name], the study biostatistician, will work closely with [name] around data management and analysis. [name] will draw on his experience with yoga research to help with issues of recruitment, enrollment and retention. Drs. [name] (attention) and [name] (pain) will provide guidance in their relative areas of expertise. [name], who is a licensed clinical psychologist, also will be responsible for clinical oversight. The timeline of major study activities is presented in Table 2.

Table 2. Study Timeline

Year 1 (2018-2019)	Year 2 (2019-2020)	Year 3 (2020-2021)	Year 4 (2021-2022)	Year 5 (2022-2023)
Original Timeline				

Set-up	Recruitment (approx. 6/month x 30 mos)	Follow-up, data lock	Dissemination	Analyses	
Regulatory	Assessment				
Hiring	Intervention delivery, fidelity (12 groups)				
Training	Data management				
Recruitment	DSMB reporting				
Revised Timeline					

 ✓ Set-up ✓ Regulatory 	
 Recruitment (approx. 6/month x 30 mos) Assessment Intervention delivery, fidelity (12 groups) Data management DSMB reporting 	Follow-up, data lock	Dissemination	Analyses	
Hiring					
Training					
Revised Timeline 2022					

 ✓ Set-up ✓ Regulatory 	
 In person recruitment → Transition → Remote recruitment Assessment Intervention delivery, fidelity Data management, including QA/QC and data lock DMC reporting 			Analyses, Dissemination	
Hiring					
Training					

Data Management

Data management and statistical analysis will be supervised by [name]. [name] is a biostatistician at the VASDHS and an Assistant Adjunct Professor in the UCSD Department of Family Medicine and Public Health. She has prior experience in VA clinical trials, including studies of yoga and PTSD, and has previously collaborated with [name]. [name] will oversee the development of the study database, which allows for automated data validation and auditing. Data will be maintained on the secure VA research server. Participant names will be held separate from data. Subjects will be assigned a unique ID number, and the single name-to-ID relational file will be kept in an encrypted form electronically and in a locked filing cabinet physically. Statistical analysis will be conducted using SPSS, R and SAS software packages. All statistical transfer routines are inherently secure via their operating platform and they contain no patient names or personal data.

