Successful past research also speaks to the acceptability yoga and similar complementary approaches in San Diego. Co-Investigator [name] has been conducting yoga research at VA San Diego since 2004, establishing the feasibility of conducting yoga research at this facility. [name] most recent RCT of yoga for VA patients with chronic low back pain easily enrolled the target of 150 VA patients within 30 months (Groessl et al., 2017). This study, which utilized the protocol to be used herein, compared hatha yoga delivered immediately or after a delay. Participants attended an average of 13 (median 15) of 24 classes, and 80% were retained at 6- and 12-weeks, with 73% retention at 6-months. Both groups showed significant change on the primary outcome measure, the Roland-Morris Disability Questionnaire. Mental health outcomes were not measured in this study, but [name] past work with pain patients showed significant change in depression and mental health related quality of life (Groessl, Weingart, Aschbacher, Pada, & Baxi, 2008).

The acceptability of a yoga and physical activity trial is also suggested by successful trials at this facility utilizing other complementary and alternative treatments for PTSD. [name] recently completed a feasibility and proof of concept study of compassion meditation (CM) for Veterans with PTSD. CM focuses on the heartfelt wish that others be free of suffering based on cultivation of a common sense of humanity. This NCCIH R34 (PI [name]) involves iterative refinement of the meditation protocol based on quantitative and qualitative data followed by a small randomized controlled trial comparing CM to a relaxation-based control. Pooled data from the nonrandomized refinement phase, which enrolled 36 participants in 4 groups, shows meaningful change in PTSD (partial eta squared = 0.27) and depression (partial eta squared = 0.19). The subsequent randomized pilot study enrolled 38 participants in CM or a relaxation condition; results are not yet available. [name] was also a co-investigator on [name] mantram repetition trials. The first enrolled 66 Veterans with PTSD in a group format (Bormann, Liu, Thorp & [name], 2012), and the second enrolled 118 Veterans in a randomized trial that delivered care one-on-one (manuscript submitted for publication). Finally, [name] recently randomized 203 Veterans with PTSD to Transcendental Meditation, Prolonged Exposure or health education (personal communication).

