Potential participants will be recruited from VA clinics (including primary care and mental health) and the community, following procedures that have been proven successful in our previous meditation and yoga trials. The initial contact for potential participants will be with a study recruiter/assessor, who will complete informed consent and conduct the evaluation for eligibility (see *Assessment*). After eligibility and consent are confirmed, the participant will complete the baseline assessment and then will have brief safety assessments every class; they will be asked to complete a total of 12 classes within 14 weeks. A follow-up will occur 12 weeks after the completion of the final class. No shows will receive a telephone follow-up. Participants will receive a payment for each assessment session (\$50 baseline part 1, \$50 baseline part 2, \$50 post-treatment part 1, \$50 post-treatment part 2, \$50 follow-up part 1, \$50 follow-up part 2 for a total of \$300; refer to Table 1).

Randomization will be done by the study statistician. In the initial phase of the trial, this was a 2:1 allocation to yoga and physical activity and took place at the individual level. Uneven allocation was planned to allow for sufficient power to accomplish the modeling proposed in Aim 2 (refer to *Sample Size*); given pandemic-related difficulties with accrual, however, the allocation will be reversed to 1:3 for the final months of the study to accomplish a minimum of 48/cell. The randomization table will be prepared prior to start of the study and revised for the new allocation strategy. Using an individual randomization strategy and continual group enrollment allows patients to begin treatment more quickly (i.e., as soon as the baseline evaluation is complete), which reduces attrition. This continual enrollment strategy is possible because the yoga and physical activity classes do not build from week to week; rather, every class provides multiple options for each pose/exercise to allow for individual differences, as is consistent with typical practice in the community. Further, sharing of personal information is minimized in this type of class, so newcomers are unlikely to cause discomfort among group members. Further, this strategy may support better retention. By allowing participants 14 weeks in which to complete 12 classes, participants will be able to make up missed classes to receive the full “dose.”

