Clinical outcomes. The **Clinician Administered PTSD Scale (CAPS-5)**; Weathers, Blake, et al., 2013) will be used to establish the PTSD diagnosis and quantify severity. This clinician-rated measure of PTSD is the “gold standard” for assessing PTSD and takes 45-60 minutes to complete. The CAPS has high internal consistency (for the DSM-IV version, alphas of 0.87 and 0.88 for the three PTSD symptom clusters and 0.95 for PTSD symptoms overall) and validity (sensitivity, specificity, efficiency, and agreement). The CAPS total score will be used as the primary measure of clinical outcome. Given our interest in exploring the effect of these interventions on symptoms that commonly co-occur with PTSD, we will also assess depression severity as measured by the 20-item **Center for Epidemiologic Studies Depression Scale Revised (CESD-R)**; Eaton, Muntaner, Smith, Tien, & Ybarra, 2004), general anxiety as measured by the 40-item **State-Trait Anxiety Inventory (STAI)**; Spielberger, Gorsuch, Lushene, Vagg, & Jacobs, 1983), anger as measured by the 35-item **State-Trait Anger Expression Inventory – II (STAXI-II)**; Spielberger, 1991) and sleep problems as measured by the 7-item **Insomnia Severity Index (ISI)**; Bastien, Vallieres, & Morin, 2001), a 7-item instrument that assesses the consequences of and distress related to insomnia, will be included as well. Finally, the **Sheehan Disability Scale (SDS)**; Sheehan, Harnett-Sheehan, & Raj, 1996), a 3-item measure of impairment in work, social and family settings, will be included. This widely-used but low-burden measure of disability has been shown to change with treatment in similar population samples (e.g., [name], Schnurr, et al., 2016).

Clinical utility. Clinical utility can be defined as the usefulness of an intervention in clinical practice and is considered to have four major dimensions (Smart, 2006). The **appropriateness** of yoga for PTSD depends on its efficacy (addressed in Aim 1) but also on the successful integration of the intervention into current care practices. **Accessibility** involves the factors involved in making yoga available to Veterans. Issues such as the usability of the manual and the way in which training can be conducted speak to **practicality**. Finally, the **acceptability** of yoga depends on its reception by key stakeholders, including Veterans and clinicians. Aspects

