	HRV		X			X	X	2
	Montreal Cognitive Assessment		X					1
	PTSD Checklist-5		X	X	X	X	X	1
	Mini International Neuropsychiatric Interview		X					1
	Emory Treatment Resistance Interview for PTSD		X			X	X	1
Clinical Outcomes	Clinician Administered PTSD Scale 5	1a	X			X	X	1
	Center for Epidemiologic Studies Depression Scale	1b	X	X	X	X	X	1
	State-Trait Anxiety Inventory	1b	X		X State only	X	X	1
	State-Trait Anger Expression Inventory	1b	X		X	X	X	1
	Insomnia Severity Index	1b	X		X	X	X	1
	Sheehan Disability Scale	1b	X		X	X	X	1
Mechanisms of Change	Attention Model							
	Philadelphia Mindfulness Scale	2a	X			X	X	1
	Digit Span	2a	X			X	X	2
	Coping Model							
	Ruminative Thought Style Questionnaire	2b	X			X	X	1
	Emotion Regulation Questionnaire	2b	X			X	X	1
	Brief Experiential Avoidance Questionnaire	2b	X			X	X	1
Distress Tolerance Scale	2b	X			X	X	1	

Intervention

Yoga. The proposed yoga program is a classical Hatha practice, which is currently used at the VA San Diego. Hatha yoga refers to practice of physical asanas, or poses, as opposed to practices that are limited to breath-work or are primarily meditative. The program is designed to minimize the risk of injury and make the poses accessible to a wide range of people (Iyengar, 1979). The manualized program (see the manual and

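### The pattern-mixture check for drop-out bias says little about CAPS as specified and does not reach people with no post-baseline CAPS; a delta-adjusted analysis should be the main check

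*Combined protocol and SAP*

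**What the plan says.** Clinical outcomes: "The CAPS total score will be used as the primary measure of clinical outcome". In Table 1 the row for "Clinician Administered PTSD Scale 5" is marked at baseline, post-treatment and follow-up; the weekly and mid-treatment cells are blank. Under Procedures, "A follow-up will occur 12 weeks after the completion of the final class", and the classes may take up to 14 weeks.

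Analytic Plan, on Hypotheses 1a and 1b: the mixed models are said to "provide overall estimates of effects by averaging over the various missing-data patterns". As a further step, "we will use the extension of the Pattern-Mixture Models", "which allows subject-to-subject heterogeneity and assess if there is bias due to drop out or missing data". Later in the same paragraph, on the mixed model: "A fully saturated treatment by time model will be utilized for inference". The plan does not define the patterns, the time function within pattern, an identifying restriction, a rule for pooling sparse patterns, or the visit at which bias is judged.

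On who is analysed, the Analytic Plan says two things. Its missing-data paragraph includes all subjects. Its closing sentences limit the analysis to randomised subjects with a baseline assessment and at least one evaluation after it.

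**The concern.** CAPS at three visits gives three monotone drop-out patterns: baseline only, baseline plus post-treatment, and complete. The first carries no information on change. The second carries none on follow-up. A pattern-mixture model can fill those gaps only with an assumption, and the plan does not say which.

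The other drop-out checks in the Analytic Plan compare groups: drop-outs with completers at baseline, and primary outcomes of people with and without missing data. Only the pattern-mixture step could show how the CAPS effect changes if missingness is not random. If it has little power, it will usually find nothing whether or not bias exists, and that could be taken as support for the primary result.

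The stake is moderate. If 20–27% of follow-up CAPS is missing and the arm difference among the unseen outcomes departs by .5 SD from what is assumed, the effect moves by .20 × .5 = .10 SD to .27 × .5 = .135 SD. That is 20–27% of the planned .5 SD effect.

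**Working it through.** The plan gives no precision or power figure for this check, so there is none to reproduce.

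**Inputs.** 48 per arm, attrition of 10% and 20%, correlations r of .2, .5 and .8, and a medium effect of .5 SD (Sample size). Two-sided .05 (Analytic Plan). As a scenario only, the site's earlier yoga trial in chronic low back pain: "80% were retained at 6- and 12-weeks, with 73% retention at 6-months" (Acceptability). Assumptions: monotone drop-out, equal variances at each visit, normal approximation.

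**1. What the data identify.** I counted the rank of the arm × pattern × time design against its number of means or coefficients.

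| Patterns | Saturated time | Linear time |
|---|---|---|
| Baseline only; baseline + post; complete | 12 of 18 | 10 of 12 |
| Baseline + post; complete | 10 of 12 | 8 of 8 |

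With saturated time, every last-visit mean of a drop-out pattern is unidentified. With linear time, the baseline + post pattern becomes estimable, but the baseline-only pattern still lacks a slope in each arm.

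**2. Expected pattern sizes per arm of 48.**

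| Scenario | Baseline only | Baseline + post | Complete |
|---|---|---|---|
| 10% total, split evenly | 2.4 | 2.4 | 43.2 |
| 20% total, split evenly | 4.8 | 4.8 | 38.4 |
| 20% total, all after post | 0 | 9.6 | 38.4 |
| Earlier trial, 80% then 73% | 48 × .20 = 9.6 | 48 × .07 = 3.4 | 48 × .73 = 35.0 |

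In the last scenario 9.6 of 13.0 drop-outs per arm have no post-baseline CAPS.

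**3. Power of a pattern-by-arm test on baseline-to-post change.** The variance of change is 2(1 − r) in SD² units. With n in the drop-out pattern and m completers per arm, SE = √[2 × 2(1 − r) × (1/n + 1/m)], and power for .5 SD is Φ(.5/SE − 1.96) + Φ(−.5/SE − 1.96).

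| n, m | r = .2 | r = .5 | r = .8 |
|---|---|---|---|
| 2.4, 43.2 | SE 1.19, 7% | SE .94, 8% | SE .59, 13% |
| 3.4, 35.0 | SE 1.02, 8% | SE .80, 10% | SE .51, 17% |
| 4.8, 38.4 | SE .87, 9% | SE .68, 11% | SE .43, 21% |
| 9.6, 38.4 | SE .65, 12% | SE .51, 16% | SE .32, 34% |

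The smallest difference detectable with 80% power is 2.8 × SE: 1.7–3.3 SD with 2.4 per arm, 1.2–2.4 SD with 4.8, and .9–1.8 SD with 9.6.

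**4. Precision of the pattern-averaged effect.** Use the earlier-trial counts, r = .5 and linear extrapolation from week 14 to week 26 (14 + 12).

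- Arm difference within the baseline + post pattern: SE = √(2 × 1/3.4) × 26/14 = 1.4 SD.
- Completers: SE = √(2 × 1/35) = .24 SD.
- Weight of the drop-out pattern, with baseline-only people left out: 3.4/38.4 = .09.
- Average: √[(.09 × 1.4)² + (.91 × .24)²] = about .25 SD.

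At r = .8 the average is .16 SD, against .15 for completers alone.

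**5. Simulated cross-check.** With 5 of 48 per arm dropping out after post-treatment, r = .5, a true effect of −.50 and no drop-out bias, 2,000 runs gave a mean of −.50 (SD .21) when follow-up was borrowed from completers, and −.49 (SD .23) with linear extrapolation. This shows that the model can be fitted. It does not show that it detects bias.

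**The case against.** A reader might infer that the check cannot work at all because the follow-up effect in drop-out patterns is not estimable. The documents do not support that. The saturated model is stated for the main inference, in a different sentence from the pattern-mixture step, and nothing says time is saturated within pattern. Linear time over the two patterns that have post-treatment data is full rank. The plan also cites a published extension whose content is not in the documents, so its own way of identifying missing cells cannot be ruled out.

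A reader might also take the 1.4 SD standard error as the precision of the check. That is the figure inside one small pattern; the averaged effect has about .25 SD.

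Further points stand. The retention figures come from a back-pain trial. People who miss only post-treatment do have follow-up CAPS, and people seen at post-treatment inform that visit fully. The plan sets no significance rule for the pattern-mixture step; its sentence treating non-significance as support for random drop-out concerns the baseline comparison. A delta grid is itself an untestable assumption.

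These points limit the claim without removing it. If follow-up values are borrowed from completers within arm, given earlier CAPS, that is the missing-at-random assumption itself and cannot reveal a departure from it. Linear extrapolation is an assumption the plan does not state. Neither reaches people with no post-baseline CAPS. A delta analysis differs in that its assumption is visible and varied.

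**Conclusion.** The concern holds as one of weak information and incomplete cover. Across 2.4–4.8 people per arm in the baseline + post pattern and r = .2 to .8, power for a .5 SD pattern-by-arm difference is about 7–21%; with 9.6 per arm it is 12–34%. A null result is therefore close to uninformative about bias. People with baseline CAPS only fall outside the check under any time function. In the earlier-trial scenario they are the larger drop-out group, and the plan is inconsistent on whether they are analysed.

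The figures rest on monotone drop-out, equal variances, a normal approximation and an assumed timing of losses. The missing CAPS change in the baseline-only pattern rests on the visit schedule alone. The documents do not show that the pattern-mixture model is impossible to fit or that its averaged estimate is unusably imprecise.

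**What to change.** Add a delta-adjusted (tipping-point) sensitivity analysis of CAPS as the main check for non-random missingness, in all randomised participants with a baseline CAPS.

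- Multiply impute missing post-treatment and follow-up CAPS under missing at random.
- Add offsets to the imputed values, varied separately by arm over a stated grid, for example 0 to 1 baseline SD.
- Report the arm difference across the grid and the offset at which the conclusion changes.

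The pattern-mixture model may stay as a supporting analysis if its patterns, time function and identifying restriction are stated. The plan should say that a non-significant pattern test is not evidence of no bias. The two Analytic Plan statements on who is analysed should be reconciled, including whether the post-baseline evaluation must be a CAPS.

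The cost is SAP wording and a short program. The grid is a judgement. The fix also brings imputation into a sensitivity analysis, although the plan lists avoiding imputation as an advantage of the mixed model; the primary analysis is unchanged.
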